10.2 Disposition of Stored Samples and Data

Access to stored samples will be limited using a locked freezer. Samples and data will be stored using codes assigned by the investigators. Data will be kept in password-protected computers. Only investigators will have access to the samples and data.

- Samples and data acquired will be kept at University of Michigan.
- Skin biopsies will be housed at University of Pittsburgh

At the completion of the protocol (termination), samples and data will be reserved for future, unspecified research if the subject has consented to analysis of their specimens outside of this protocol. If the subject doesn't consent to long term storage, the samples will be destroyed at the end of the study.

Additionally, subjects may decide at any point during the study not to have their samples stored. In this case, the principal investigator will destroy all known remaining samples and report what was done to both the subject and to the IRB. This decision will not affect the subject's participation in this protocol.

1.1. Primary Endpoint

Objective: To demonstrate acceptable safety and tolerability of tofacitinib in early dcSSc.

The primary endpoint is the proportion of participants who experience Grade 3 or higher (more severe) adverse events that occur at or before Week 24 (double-blind phase).

1.1.1. Primary Analysis of the Primary Endpoint.

The proportion of subjects in the safety population (see Section 2.1) with at least one Grade 3 or higher adverse event that begins at or before Week 24, the double-blind phase of the trial, will be calculated and compared for each of the study treatment arms.

1.1.2. Secondary Analysis of the Primary Endpoint.

To assess the robustness of the results for the primary analysis, an analysis of the total number of Grade 3 (severe) or higher adverse events that begin at or before Week 24 will also be compared for each of the study treatment arms.

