2. STUDY OUTCOMES

2.1 Primary Outcomes

The **primary study endpoint** will be the proportion of participants who experience Grade 3 (severe) or higher adverse events that occur at or before Week 24.

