7.7 Non-Serious Adverse Event Collection and Reporting

The collection of non-serious adverse event (NSAE) information should begin at initiation of study drug. NSAE information should also be collected from the start of a placebo lead-in period or other observational period intended to establish a baseline status for the participants. NSAEs should be followed to resolution or stabilization, or reported as SAEs if they become serious.

Follow-up is also required for NSAEs that cause interruption or discontinuation of study drug, or those that are present at the end of study treatment as appropriate. All identified NSAEs must be documented appropriately and reported per the sites individual local guidelines.

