2.2. Analyses of Primary Endpoint

The primary analysis is a comparison of the percentage of subjects with Grade 3 adverse events that begin within the first 24 Weeks following initiation of study treatment between tofacitinib and placebo. The analysis will be performed on the safety population. The test will be performed using Fisher's Exact Test, given that the largest possible number of patients affected are 10 and 5, respectively, for tofacitinib and placebo. The number and percentage of patients with at least one Grade 3 adverse event will be provided along with Clopper Pearson Exact confidence intervals for proportions at the 90% threshold.

2.2.1. Primary Analysis of the Primary Endpoint.

Proportion of patients with at least one Grade 3 adverse event within the first 24 Weeks

Analysis Set	Safety Population		
Methods	Fisher's Exact Test		
	Clopper Pearson Exact Confidence Intervals		
Results	 Number and percentage of subjects with at least one Grade 3 adverse event in the first 24 weeks 90% confidence interval for proportions P-value from Fisher's Exact Test 		

2.2.2. Secondary Analysis of the Primary Endpoint.

A sensitivity analysis will be performed to assess how the total number of Grade 3 or higher adverse events, rather than just the proportion of patients experiencing the events, affect the conclusions of the analysis of the primary endpoint. The analysis will employ Poisson Regression methodology, offset for time in the study (the lesser of 24 weeks, or withdrawal from the trial).

Analysis Set	Safety Population		
Methods	Poisson Regression offset for time in the study (the lesser of 24 weeks or		
	withdrawal from the trial)		
Dependent	Number of grade 3 or higher adverse events experienced within the first		
Variable	24 weeks on a per patient basis.		
Covariate	Treatment		
Results • Total number of Grade 3 adverse event in the first 24 week			
	 Relative risk of tofacitinib to placebo. 		
	 90% confidence interval for relative risk 		
	P-value for treatment effect		

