# of SAEs		
# of Subjects with SAEs		
# of Subjects		
SAEs per Subject		
% of Subjects with SAEs		

Table 9: TOFA Proportion of Subjects with SAEs by Severity Grade. Safety Population.

System Organ Class Preferred Term	Tofacitinib N=10 n (%) [1]	Placebo N=5 n (%) [1]
Total Events		
Total Subjects With At Least One Event		
Grade 1		
Grade 2		
Grade 3		
Grade 4		
Grade 5		
Grades 3-5		

[1] Percentages are 100*n/N.

The severity grade shown is the greatest grade reported per event for a particular Subject (Grade 1 < Grade 2 < Grade 3 < Grade 4 < Grade 5).

Listing 3: TOFA Listing of SAEs. Safety Population.

Tro	eatment	Subject ID	SAE#	New SAE since (Date of last report)	SAE Brief Description (Verbatim Term)	Treatment Emergent?	SAE Start Date	SAE Stop Date	Days from Start of Study Medication	Severity Grade	Relationshi p to Study Treatment	Outcome	Study Drug Action Taken	Study Drug Stop Date	Study Drug Start Date	

There were no SAEs reported as of the data cutoff date.

Treatment emergent adverse events are AEs that are began after the first dose of study medication.

Note: Double-Blind Treatment is expected to last 24 Weeks (168 Days). Those SAEs that started >= Day 169 are assumed to have occurred during the Open Label phase.

Data cutoff date: DDMMYY

Listing 4: TOFA Listing of Deaths. Safety Population

Treatment	Subject ID	SAE#	New SAE since Aug 4, 2017	SAE Primary Category	SAE Description (Verbatim Term)	Treatment Emergent?	SAE Start Date	SAE Stop Date	Days from Start of Study Medication	Severity Grade	Relationship to Study Treatment	Outcome	Study Drug Action Taken	Treatment Required

Conditional Note: There were no deaths reported as of the data cutoff date.

Treatment emergent adverse events are AEs that began after the first dose of study medication.

Table 10: TOFA Proportion of Subjects with Adverse Events by Primary Category. Safety Population.

Preferred Term	Tofacitinib n (%) [1]	Placebo n (%) [1]

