# of Safety Patients		
# of AEs		
# of Subjects with AEs		
% of Subjects with AEs		
Severity Grade		
No Adverse Events		
Mild		
Moderate		

[1] Percentages are 100*n/N.

The severity shown is the greatest reported per event for a particular Subject (Mild < Moderate < Severe).

Data cutoff date: DDMMYY

Listing 5: TOFA Listing of Treatment Emergent Adverse Events. Safety Population.

Treatment	Subject ID	New AE Since March 5, 2018	CTCAE Classificaiton	AE Primary Category	AE Start Date	AE End Date	Days from Start of Study Medication	Severity	Relationship to Study Treatment	Outcome	Expected / Unexpected	Study Drug Action Taken	SAE?	Worsening of SSC?

Treatment	Subject ID	New AE Since March 5, 2018	CTCAE Classificaiton	AE Primary Category	AE Start Date	AE End Date	Days from Start of Study Medication	Severity	Relationship to Study Treatment	Outcome	Expected / Unexpected	Study Drug Action Taken	SAE?	Worsening of SSC?

Data cutoff date:DDMMYY

Note: Double-Blind Treatment is expected to last 24 Weeks (168 Days). Those AEs that started >= Day 169 are assumed to have occurred during the Open Label phase.

Table 12: Adverse Events of Special Interest. Safety Population.

Preferred Term Category	Tofacitinib N=10 n (%) [1]	Placebo N=5 n(%) [1]
Total Events		
Total Subjects With At Least One Event		
Herpes Zoster		
Malignancies		
Serious Infections		
Lab Value Abnormalities		
Lymphocytes <500cells mm3		
ANC <500cells mm3		
AST/ALT > 3xULN		
Hy's Law Criteria Met		
Hb drop >2gm/dL		
Increase in HDL/LDL > 50%		
Increase in Serum Creatinine > 50%		

[1] Percentages are 100*n/N. Data cutoff date: DDMMYY

The following set of Figures will be of this format:

[figure not shown]

Figure 1: TOFA Spaghetti Plots of Hemoglobin Over Time by Treatment Figure 2: TOFA Spaghetti Plots of WBC Over Time by Treatment

Figure 3: TOFA Spaghetti Plots of Creatinine Over Time by Treatment

Figure 4: TOFA Spaghetti Plots of Lymphoctyes %Over Time by Treatment

Figure 5: TOFA Spaghetti Plots of Neutrophil % Over Time by Treatment

Figure 6: TOFA Spaghetti Plots of ALT Over Time by Treatment

Figure 7: TOFA Spaghetti Plots of AST Over Time by Treatment

Figure 8: TOFA Spaghetti Plots of Total Cholesterol Over Time by Treatment

Figure 9: TOFA Spaghetti Plots of Triglycerides Over Time by Treatment

Figure 10: TOFA Spaghetti Plots of LDL Over Time by Treatment

Figure 11: TOFA Spaghetti Plots of HDL Over Time by Treatment

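### The SAP dates adverse events by onset but sets no date by which Grade 3 must be reached, so severity reached on open-label tofacitinib can enter the Week 24 primary comparison.

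*SAP*

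**What the plan says.** Protocol 2.1 defines the primary endpoint as "the proportion of participants who experience Grade 3 (severe) or higher adverse events that occur at or before Week 24". SAP 1.1 repeats that definition and adds that the period is the double-blind phase.

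The operational text dates events by onset. SAP 1.1.1 counts subjects with "at least one Grade 3 or higher adverse event that begins at or before Week 24", and SAP 2.2 compares "Grade 3 adverse events that begin within the first 24 Weeks following initiation of study treatment". SAP 1.2.2 applies the same rule at the Grade 2 threshold: the event must begin by the time point, and the grade carries no time limit. The Poisson analysis in SAP 2.2.2 uses a third wording, events experienced within 24 weeks, with follow-up time capped at 24 weeks.

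Only two notes in the SAP say which grade to use. Under Table 9 (serious adverse events by grade): "The severity grade shown is the greatest grade reported per event for a particular Subject". Under Table 11 (all adverse events by severity): "The severity shown is the greatest reported per event for a particular Subject". Neither sets a time limit. Table 13, the shell for the primary outcome, has no note on grade.

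Listings 3 and 5 each have one start date column and one severity column. The Listing 5 note assigns phase by start day: "Those AEs that started >= Day 169 are assumed to have occurred during the Open Label phase". Protocol 7.5 lists onset, duration and intensity for capture, but no date of grade change. Protocol 7.7 continues follow-up after onset: "NSAEs should be followed to resolution or stabilization, or reported as SAEs if they become serious". Under Protocol 4.1, subjects in both arms may take open-label tofacitinib after Week 24.

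**The concern.** The endpoint definition asks about severity experienced by Week 24. The counting rule asks only whether the event had started by then. The two agree when an event keeps its starting grade or worsens before Week 24. They can differ when an event starts mild or moderate during blinded treatment and becomes severe after the switch to open-label drug.

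At stake is the trial's primary safety contrast, in which the control arm is five people. For a placebo subject, severity that developed on tofacitinib would be charged to placebo. For a tofacitinib subject, severity from beyond 24 weeks of exposure would be credited to the 24-week window. In SAP 2.2.2 the mismatch also reaches the rate, because the denominator stops at 24 weeks while the severity that qualifies an event may arise later.

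**Working it through.** **Following one event through the rule.** Take an event with onset in Week 22 at Grade 2 that reaches Grade 3 in Week 30.

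- Onset day: 22 × 7 = 154, before Day 169, so the Listing 5 note places it in the double-blind phase.
- Day Grade 3 is reached: 30 × 7 = 210, during open-label treatment.
- If the event is one record carrying its greatest grade, its row reads start Day 154, Grade 3. That satisfies SAP 1.1.1 and 2.2.
- Under Protocol 2.1 and SAP 1.1, the subject had not experienced a Grade 3 event by Day 168 (24 × 7).

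The onset rule is written. The single record carrying the greatest grade is an assumption, consistent with the listing layout and the notes to Tables 9 and 11 but not stated for the primary endpoint.

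**Weight of one subject.** Protocol 8.1 gives 10 tofacitinib and 5 placebo subjects. One placebo subject is 1/5 = 20 percentage points; one tofacitinib subject is 1/10 = 10.

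**Check of the test.** The plan gives no figure on this point. Its nearest figure is the power claim in Protocol 8.1: at least 80% for 20% vs 86%, 10% vs 79% and 5% vs 74%, two-sided 10%. Enumerating all 11 × 6 outcomes and rejecting when two-sided Fisher p ≤ 0.10 gives 80.2%, 80.5% and 81.0%. The claim is reproduced, and it does not depend on the counting rule.

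**Sensitivity of the primary test.** The two-sided p sums the hypergeometric probabilities no larger than that of the observed table.

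- 6/10 vs 0/5, 6 events in 15: (210 + 10)/5005 = 0.044.
- 6/10 vs 1/5, 7 events in 15: (1050 + 120 + 600 + 45)/6435 = 0.282.

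One placebo subject who worsens late, counted or not:

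| Tofacitinib | Placebo, counted | p | Placebo, not counted | p |
|---|---|---|---|---|
| 6/10 | 1/5 | 0.282 | 0/5 | 0.044 |
| 7/10 | 1/5 | 0.119 | 0/5 | 0.026 |
| 8/10 | 2/5 | 0.251 | 1/5 | 0.089 |
| 2/10 | 1/5 | 1.00 | 0/5 | 0.52 |

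One tofacitinib subject who worsens late, placebo 0/5: counted, 6/10 gives p=0.044; not counted, 5/10 gives (252 + 50 + 1)/3003 = 0.101. This shift runs the opposite way to the placebo shift.

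**Interval estimates.** The 90% Clopper-Pearson interval for placebo is 0% to 45.1% at 0/5 (upper limit 1 − 0.05^(1/5)) and 1.0% to 65.7% at 1/5 (lower limit 1 − 0.95^(1/5)). SAP 2.2 plans this interval as a result, so reporting changes even where no p-value crosses 0.10.

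The event rates are illustrative. The documents give no expected rates beyond the power examples and no count of events that worsen after Week 24.

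**The case against.** A reader might infer that the SAP grades the primary endpoint by the worst grade an event ever reached. It does not say so. The greatest-grade notes belong to Tables 9 and 11, which are descriptive and have no Week 24 window; SAP 1.1.1, SAP 2.2 and Table 13 are silent. Read with SAP 1.1 directly above it, 1.1.1 can mean that the Grade 3 episode itself must begin by Week 24.

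Recording practice could also resolve the matter. Protocol 7.1 treats worsening of a pre-existing condition as an adverse event, so a worsened event might become a new record with its own onset. Protocol 7.7 has events that become serious reported as serious adverse events, and Listing 3 gives each of those its own number and start date. These points stand as possibilities. But no text requires a new record on worsening, and seriousness (Protocol 7.2) and grade (Protocol 7.4) are defined separately, so the serious-event route need not date every rise to Grade 3.

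A reader might also infer that the rule biases the comparison toward no difference. The documents do not support a direction: the same rule covers the ten tofacitinib subjects, and late worsening there raises that arm's rate.

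The examples that cross 0.10 need high tofacitinib rates. Protocol 8 calls p-values hypothesis generating, and many events open at Week 24 will never reach Grade 3. All of this limits the size of the point without supplying the missing rule.

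**Conclusion.** The point holds as a gap in the counting rule. The SAP dates events by onset, leaves the timing of the grade open, and plans for no date of grade change. A programmer following it could count open-label severity in the double-blind primary comparison, contrary to the endpoint defined in Protocol 2.1 and SAP 1.1.

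The size is 20 points per affected placebo subject and 10 per affected tofacitinib subject. Net direction is uncertain and the number affected is unknown. The misattribution requires that the event stays one record, that the grade reported is the greatest, that Grade 3 is first reached after the switch, and that the subject has no other qualifying event.

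The Week 12 analysis has the same timing gap but no treatment switch, so no exposure is charged to the wrong arm there. This is a low-cost improvement worth making; it does not show that the primary result will be wrong.

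**What to change.** In SAP 1.1.1, 1.1.2, 1.2.1, 1.2.2, 2.2, 2.2.2, 2.3.1 and 2.3.2, and in the matching table shells including Table 13, count an event by the date it first reached the threshold grade: Grade 3, or Grade 2 for 1.2.2. For the Week 24 analyses, require that date to be at or before Week 24 and before the first open-label dose. The second condition is needed because Protocol 6.1 allows visits ±10 days, so the Week 24 visit, at which open-label drug is dispensed, may fall as early as Day 168 − 10 = 158.

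Record the date of grade change on the existing adverse event record. Opening a new row could turn one Grade 2 event that rises to Grade 3 into two events in the Grade 2 or higher counts. Query every adverse event ongoing at Week 12 and at Week 24 for the date of any later rise in grade.

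The cost is SAP wording, one extra date per worsened event, and a few queries in 15 subjects. The rule should be set before unblinding, the deadline Protocol 8 gives for finalizing the SAP.

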1.2. Secondary Endpoints

1.2.1. Secondary Endpoint. Analyses of the Primary Endpoint Over Time.

The analyses of the primary endpoint described in sections 1.1.1 and 1.1.2 will be repeated at Weeks 12 to assess the time course of the safety profile as defined by the occurrence of Grade 3 or higher adverse events.

1.2.2. Secondary Endpoint. Analyses of the Adverse Events at the Grade 2 Threshold.

The analyses described in sections 1.1.1, 1.1.2 and 1.2.1 will be repeated for adverse events beginning at or before the time point of interest that are assessed as at least Grade 2 (moderate) severity.

1.2.3. Secondary Endpoint. % of Subjects with Adverse Events of Special Interest (AESI).

The proportion of subjects in the safety population experiencing an AESI will be compared between the two study treatment arms. Comparisons will be made for at least one AESI of any type, as well as for each of the events that are considered to be of special interest individually. Separate analyses will be performed for AESIs that occur at or before Weeks 12 and 24. AESIs are defined to be any one of herpes zoster, malignancy, serious infection, lymphocytes <500cells mm³, ANC <500cells mm³, AST > 3xULN, ALT > 3xULN, Hy's Law criteria met, Hemoglobin drop > 2mg/dL, increase in HDL/LDL ratio > 50%, or an increase in serum creatinine > 50%.

1.2.4. Secondary Endpoint. Change from Baseline in the Modified Rodnan Skin Score (mRSS).

Change from baseline in the mRSS total score will be compared between the two treatment arms to assess skin thickness relative to the initiation of study treatment at the various time points. The analysis will be performed separately at Weeks 12 and 24 on subjects in the modified intent-to-treat (mITT) population (see section 2.1).

1.2.5. Secondary Endpoint. Provisional American College of Rheumatology Combined Response Index in Systemic Sclerosis CRISS will be compared between the two treatment arms separately at Weeks 12 and 24 on subjects in the modified intent-to-treat (mITT) population (see section 2.1).

1.2.6. Secondary Endpoint. % of Responders as Defined by the mRSS.

Subjects in the mITT population will be assessed for reaching clinical thresholds of decreased skin thickness over time as defined by a percentage reduction in the mRSS from baseline. Time points assessed will be Weeks 12 and 24, and analyzed separately. Within each of these time points, separate analyses will be performed for decreases (responder definition) of at least 20, 40, and 60% relative to the baseline mRSS total score.

1.2.7. Secondary Endpoint. Change from Baseline in the mRSS sub-scores.

Change from baseline in the mRSS representative score and maximum score will be compared between the two study treatment arms for the mITT population of subjects at Weeks 12 and 24 separately.

1.2.8. Secondary Endpoint. Change from Baseline in Physician Global Health Assessment.

Change from baseline in the physician's global health assessment will be compared between the two study treatment arms for the mITT population of subjects at Weeks 12 and 24 separately, to determine overall progression of disease severity as determined by the subject's physician.

1.2.9. Secondary Endpoint. Change from Baseline in Patient Global Health Assessment.

Change from baseline in the patient's global health assessment will be compared between the two study treatment arms for the mITT population of subjects at Weeks 12 and 24 separately, to determine overall progression of disease severity as determined by the subject.

1.2.10. Secondary Endpoint. Change from Baseline in Health Related Quality of Life (HRQoL) using the Patient-Reported Outcomes Measurement Information System (PROMIS-29).

Change from baseline in the HRQoL total score will be compared between the two study treatment arms for the mITT population of subjects at Weeks 12 and 24 separately to determine perceived overall changes in quality of life since the initiation of study treatment as determined by the subject.

1.2.11. Secondary Endpoint. Change from Baseline in the Scleroderma Health Assessment Questionnaire-Disability Index (SHAQ-DI).

Change from baseline in the SHAQ-DI total score will be compared between the two study treatment arms for the mITT population of subjects at Weeks 12 and 24 separately to determine perceived overall changes in the subject's functional ability since the initiation of study treatment as determined by the subject.

1.2.12. Secondary Endpoint. Change from Baseline in the UCLA SCTC Gastrointestinal Symptoms Total Score (GIT).

Change from baseline in the UCLA SCTC GIT will be compared between the two study treatment arms for the mITT population of subjects at Weeks 12 and 24 separately to determine changes in the subject's gastrointestinal symptoms since the initiation of study treatment.

1.2.13. Secondary Endpoint. Change from Baseline in the PRO for Scleroderma-related Skin Symptoms (PRO-SRSS) Total Score.

Change from baseline in the PRO-SRSS will be compared between the two study treatment arms for the mITT population of subjects at Weeks 12 and 24 separately to determine changes in the subject's overall skin symptoms since the initiation of study treatment.

1.2.14. Secondary Endpoint. Change from Screening in Pulmonary Function Tests (PFT).

Change from screening PFTs will be compared between the two study treatment arms for the mITT population of subjects at Weeks 12 and 24 separately for each of percent predicted FVC, FEV and DLCO.

1.2.15. Secondary Endpoint. Change from Screening to Week 24 in Left Ventricular Ejection Fraction (Maximum of Range).

Change from screening ejection fraction will be compared between the two study treatment arms for the mITT population of subjects at Week 24.

1.2.16. Secondary Endpoint. Change from Screening to Week 24 in Tricuspid Regurgitation Jet.

Change from screening tricuspid regurgitation jet will be compared between the two study treatment arms for the mITT population of subjects at Week 24.

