2.2 Secondary Outcomes

The **secondary study endpoints** will include:

- Number of Grade 3(severe) or higher adverse events that occur at or before Weeks 12, 36, and 48

- Number of Grade 2 (moderate) or higher adverse events that occur at or before Weeks 12, 24, 36, and 48
- Number of AE's of special interest (AESI) at Weeks 12, 24, 36, and 48
- Change in modified Rodnan Skin Score (mRSS) at Weeks 12, 24, 36, and 48
- Provisional American College of Rheumatology Combined Response Index in Systemic Sclerosis at Weeks 12 , 24, and 48.

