8.2 Statistical Analyses

8.2.1 Safety Outcomes

All safety analyses will be performed on the Safety Population, defined as all subjects who were randomized and received at least one dose of the study drug. Subjects will be analyzed by the treatment received.

Safety measures including AEs, clinical laboratory tests, vital signs, ECG, physical exams, and concomitant medication usage will be summarized descriptively. For quantitative variables, descriptive statistics including number of observations, mean, median, standard deviation and range will be given for the values themselves as well as for change from baseline by treatment group at each study visit. Qualitative variables will be summarized using counts and percentages by treatment group at each study visit.

The primary endpoint is the proportion of participants who experience a Grade 3 or higher adverse event at or before Week 24 and will be compared between the two treatment groups using an exact Fisher's exact test. Exact 90% confidence intervals will be calculated to estimate the incidence of the adverse events (both primary and secondary endpoints) for each treatment group. Similar methods will be used for the secondary safety endpoints. Treatment comparisons for quantitative safety outcomes will be made using two-sample t-tests or their nonparametric counterparts (e.g., Wilcoxon rank sum test). The number (counts) of adverse events will also be compared between treatments for select adverse events (e.g., Grade 3 or higher adverse events at or before Week 24, adverse events of special interest).

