2.3. Analyses of Secondary Endpoints

2.3.1. Analyses of the primary endpoint over time.

The secondary analyses is a comparison of the percentage of subjects with Grade 3 adverse events that begin within the first 12, 36, and 48 Weeks, respectively, following initiation of study treatment between tofacitinib and placebo. Each of the time points is a standalone analysis, utilizing the methodology described for the primary analysis of the primary endpoint in section 2.2.1

Analysis Set	Safety Population
Time Points	2.3.1a: Week 12,
	2.3.1b: Week 36,
	2.3.1c: Week 46
Methods Fisher's Exact Test	
	Clopper Pearson Exact Confidence Intervals

Results	•	Number and percentage of subjects with at least one Grade 3	
adverse event up to and including the time point of ir		adverse event up to and including the time point of interest	
	•	90% confidence interval for proportions	
	•	P-value from Fisher's Exact Test	

2.3.2. Secondary analyses of the primary endpoint over time.

Secondary analyses will be performed over time (Weeks 12, 36 and 48) using the same methodology described in section 2.2.2 to explore treatment differences in the total number of Grade 3 or higher adverse events over time. The offset for time in study will be the lesser of the withdrawal date from the trial or the time point of interest.

Analysis Set	Safety Population		
Methods	Poisson Regression offset for time in the study (the lesser of the time		
	point of interest or withdrawal from the trial)		
Time Points	2.3.2a: Week 12,		
	2.3.2b: Week 36,		
	2.3.2c: Week 46		
Dependent	Number of grade 3 or higher adverse events experienced within the time		
Variable	point of interest on a per patient basis.		
Covariate	Treatment		
Results	Total number of Grade 3 adverse event within the time point of		
interest.			
	Relative risk of tofacitinib to placebo.		
	90% confidence interval for relative risk		
	P-value for treatment effect		

2.3.3. Secondary analyses for proportion of subjects.

The proportion of subjects in the specified populations above will be compared between the two study treatment arms at the specified time points utilizing Fisher's Exact Test and Clopper Pearson confidence intervals to describe treatment differences.

Analysis Set	See Above
Time Points	See Above

Parameters	Adverse events of special interest		
	mRSS responders		
Methods	Fisher's Exact Test		
	Clopper Pearson Exact Confidence Intervals		

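### The protocol promises a between-arm comparison of AESI counts at four weeks, but the SAP compares only the proportion of subjects with an AESI

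*SAP*

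**What the plan says.** **Protocol.** Section 2.2 lists as a secondary endpoint "Number of AE's of special interest (AESI) at Weeks 12, 24, 36, and 48", and the synopsis does the same. Section 8.2.1 sets out Fisher's test and exact 90% intervals for the primary endpoint and continues: "Similar methods will be used for the secondary safety endpoints". It then adds a separate commitment: "The number (counts) of adverse events will also be compared between treatments for select adverse events". The examples it gives are "Grade 3 or higher adverse events at or before Week 24, adverse events of special interest".

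**SAP.** Section 1.2.3 defines the AESI endpoint as a percentage of subjects: "The proportion of subjects in the safety population experiencing an AESI will be compared between the two study treatment arms". The comparison is made for any AESI and for each type separately. Section 2.3.3 assigns AESIs to a comparison "utilizing Fisher's Exact Test and Clopper Pearson confidence intervals to describe treatment differences". Tables 29-32 (Weeks 12, 24, 36 and 48) have rows for subjects, intervals and p-values, and none for events.

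For Grade 3+ events, SAP 2.2.2 adds a count analysis: "The analysis will employ Poisson Regression methodology, offset for time in the study". SAP 2.3.2 repeats it at other weeks, and SAP 1.2.2 extends it to Grade 2+ events. Table 12 has a row for total AESI events by arm, without an interval or test.

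**The concern.** A number of events and a proportion of subjects are different quantities. Two arms can have the same proportion affected and very different event totals. The protocol keeps both: the word *also* in 8.2.1 makes the count comparison an addition to the proportion methods. If the SAP is followed as written, one listed secondary endpoint is not reported in its stated form or at its stated weeks, and one promised comparison is not made. Anyone checking results against Protocol 2.2 would find an unexplained change of endpoint, in a trial whose stated purpose is safety and tolerability.

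**Working it through.** **1. The texts side by side.**

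| Event family | Protocol endpoint | SAP proportion analysis | SAP count analysis |
|---|---|---|---|
| Grade 3+ | Proportion at Week 24; number at Weeks 12, 36, 48 | Fisher, exact intervals (2.2.1, 2.3.1) | Poisson (2.2.2, 2.3.2; Tables 14, 16, 18, 20) |
| Grade 2+ | Number at Weeks 12, 24, 36, 48 | Fisher, exact intervals (1.2.2) | Poisson (1.2.2; Tables 22, 24, 26, 28) |
| AESI | Number at Weeks 12, 24, 36, 48 | Fisher, exact intervals (1.2.3, 2.3.3; Tables 29-32) | None |

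AESIs are the only one of the three families left without a count analysis.

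**2. Does Table 12 fill the gap?** No. It has no week cutoff, person-time, interval or comparison. The note to SAP Listing 5 assigns events from Day 169 to the open-label phase, when subjects randomized to placebo may take tofacitinib. A total without a cutoff can mix randomized and open-label events.

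**3. How the two measures can diverge (assumed data).** The documents state no AESI power or sample-size figure to reproduce. Assume 4 of 10 tofacitinib and 2 of 5 placebo subjects have an AESI, all are followed for 24 weeks, and each affected placebo subject has one event. Both proportions are 40%, so Fisher p = 1.00 however many events occur. Suppose each affected tofacitinib subject has 4 events, giving 16 vs 2:

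- Poisson rate ratio = (16/10)/(2/5) = 4.0. SE of the log = √(1/16 + 1/2) = 0.75. z = ln 4/0.75 = 1.85, p = 0.065. 90% CI = exp(1.386 ± 1.645 × 0.75) = 1.16 to 13.7.
- Overdispersion check: Pearson χ² = 24 (tofacitinib) + 3 (placebo) = 27 on 13 df, scale 2.08. SE = 0.75 × √2.08 = 1.08, z = 1.28, p = 0.20.
- Exact permutation of subject counts over all C(15,5) = 3,003 splits. With s the total in the group of five, the difference in means is 1.8 − 0.3s, observed as 1.2. Splits at least as extreme have s ≤ 2 (462 splits) or s ≥ 10 (220 + 11 + 54 = 285). p = 747/3,003 = 0.25.

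The count shows a contrast that the proportion cannot, but unscaled Poisson overstates the evidence when events cluster.

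**4. Is there power to gain?** Fisher power is Σ P(a)P(b) over outcomes with p ≤ 0.10, where a ~ Bin(10, 1 − e^−λT) and b ~ Bin(5, 1 − e^−λP). The same enumeration applied to the protocol's Grade 3+ examples gives 80.2%, 80.5% and 81.0%, matching its claim of at least 80%. Permutation power is from 4,000 simulated trials per setting. The rates are assumptions.

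| AESIs per subject, tofacitinib vs placebo | Fisher | Permutation on counts |
|---|---|---|
| 3 vs 1 | about 45% | about 73% |
| 2 vs 0.5 | about 57% | about 65% |
| 1.5 vs 0.5 | about 37% | about 39% |
| 0.6 vs 0.2 | about 11% | about 11% |
| 0.3 vs 0.1 | about 2% | about 2% |
| 3 vs 1, strong clustering (negative binomial, k = 1) | about 21% | about 22% |

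With equal rates the permutation test stayed below its nominal 10% (up to about 9%).

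**5. Where might the rate lie?** Protocol 1.2.5 gives rheumatoid arthritis figures for some AESI types. Over 24 weeks (24/52 year):

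- serious infection: 0.027 × 24/52 = 0.0125
- malignancy: 0.004 × 24/52 = 0.0018
- lymphocytes <500: 0.0004
- ANC <500: 0
- ALT >3×ULN 0.013 and AST >3×ULN 0.005 (0-3 months)
- creatinine: up to 0.02 (long-term discontinuations)

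The sum is about 0.05 per subject. It mixes follow-up periods and doses, and has no usable figure for zoster, haemoglobin or lipid AESIs. The rate in systemic sclerosis may be higher.

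**The case against.** A reader might infer that AESI counts are never analysed at all. The documents do not support that: Table 12 tabulates total events by arm. What is missing is the comparison and the figure by week.

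A reader might also infer that a subject with several AESIs always disappears into one yes/no answer. That is too strong. SAP 1.2.3 tests each type separately, so a subject with zoster, lymphopenia and raised ALT appears in three rows. Only repeats of the same type, and the combined burden per subject, are lost. Same-type repeats are also limited: Protocol 7.5.1 requires laboratory AESIs to be confirmed by repeat testing, Protocol 7.8 halts dosing for several of them, and lipids are drawn only once between screening and Week 30.

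A third inference is that the SAP gives up substantial power. The table above shows a clear gain only at high, unclustered rates. It shows none at 0.6 vs 0.2 or below, and almost none when events cluster in the same subjects, which is the very pattern that makes counts look attractive.

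The strongest defence is that Protocol 8.2.1 supports proportion methods for secondary safety endpoints, Protocol 8 leaves detail to the SAP, and p-values are hypothesis-generating. That justifies the Fisher analysis and limits the consequence. It does not justify dropping the count comparison, which the protocol states separately and the SAP keeps for the other two families. Nor do the documents show that the omission was deliberate; they give no reason either way.

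**Conclusion.** The mismatch stands on the text alone. Following the SAP yields neither the number of AESIs by week nor the between-arm comparison of counts that the protocol promises. The proportion analysis is sound and should stay.

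This is a minor point. It changes no sample size and not the primary endpoint, and no AESI rate in this population is given from which to predict an effect on conclusions. The 16 vs 2 example and the power table rest on assumed rates. They show what a count can add and how little it may add, and are not a forecast. The conclusion does not depend on them.

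**What to change.** Extend the count analysis in SAP 2.2.2 and 2.3.2 to AESIs, and add it to SAP 1.2.3 with matching shells:

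- **Weeks 12 and 24:** events, person-time and rate by arm, with the Poisson rate ratio and 90% interval. This is the randomized comparison.
- **Weeks 36 and 48:** the same quantities in the supplemental tables, labelled as including open-label exposure.
- **Counting rule:** one event per AESI episode, not per abnormal visit, with the start and end of a laboratory episode defined before unblinding.
- **Check:** an exact permutation test on subject-level counts beside the Poisson result, because of overdispersion and possible zero cells.
- **Keep** the proportion analysis in Tables 29-32.

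If the sponsor prefers proportions only, the SAP should at least state and justify the departure from Protocol 2.2 and 8.2.1.

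The cost is one table per time point from data already collected, plus the episode rule. The gain is agreement with the protocol, with little or no added power if AESIs are rare or concentrated in a few subjects.
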